# Figure 1Effect of ascending concentrations of Coversin on complement activation in
blood from a PNH patient with Type III cells

complement mediated lysis of Type III RBCs

P4

% р5

CD59 PE B585/42-A

# Figure 2 Comparison of Coversin 10µg/mL and Soliris® 50µg/mL on blood from a patient with Type III cells

Effect of rVA576 on PNH Blood 2. Patient with Type III (complete deficiency) & normal red cells – Not on eculizumab

10 µg / ml (molar equivalent of eculizumab in B)

Figure 3 CH50 activity in 6 normal subjects at the highest dose (0.57mg/kg) used in a Phase I single ascending dose (SAD) study following subcutaneous injection of Coversin

0.57mg/kg Change from baseline (individual)

A single ascending dose (SAD) Phase I clinical trial of Coversin, administered by s.c. injection, has been carried out to validate this route of administration and to confirm the dose needed to totally inhibit all C5 in the vascular compartment.

Page 25 of 84 AKARI Confidential

#### Phase 1b Trial AK577

A Phase 1b dose range finding study (AK577) was conducted in which 4 cohorts of healthy volunteer subjects were studied. All subjects received an ablating dose of 4 x 30 mg doses 12 hourly (or the placebo equivalent), before going on to receive maintenance doses at 1 of 3 dose levels for a further 5-days, or in the case of Cohort 4 for a further 19 days.

There were 6 subjects in each of Cohort 1 (30 mg once a day maintenance dose), Cohort 2 (22.5 mg once a day maintenance dose) and Cohort 3 (15 mg once a day maintenance dose) with 4 active subjects receiving rVA576 and 2 subjects receiving placebo in each cohort. Cohorts 1, 2 and 3 subjects were followed during a 2-day recovery period from Day 7 to 9.

Cohort 4 (comprising 4 active subjects only) received the same ablating dose as Cohorts 1, 2 and 3 and a maintenance dose of 22.5 mg once a day for 19 days. Cohort 4 subjects were followed during a 7-day recovery period from Day 21 to 28.

As shown in Figure 4 the ablating dose rapidly reduced terminal complement activity (TCA) below the lower limit of quantification (LLOQ) for the ELISA CH50 assay and TCA was essentially completely inhibited at maintenance doses of 30 mg once daily for 5 days and 22.5 once daily for both 5 and 19 days.

One subject stopped treatment in Cohort 1. The subject, who had received 3 doses of rVA576 and 4 doses of ciprofloxacin, experienced significantly raised creatinine kinase (CK) and serum myoglobin level on Day 2. The Investigator considered that this adverse event (AE) was reported as rhabdomyolysis. The Investigator considered it to be related to the administration of ciprofloxacin, as it is a known but rare side effect of the drug.

In general, all adverse events were mild to moderate in intensity and all resolved. For further details, please refer to the IB and Table 3.

Figure 4AK 577 Mean (+/-SD) CH50-Time Plot

### 2.3 Dose and Dose Interval Considerations

The pharmacokinetics (PK) and pharmacodynamics (PD) of Coversin in humans and laboratory animals is different in a number of ways. In part, this is due to humans having a greater percentage of subcutaneous fat compared to laboratory animals including NHP, which leads to both slower absorption, as drug remains in the injection site for longer.

It has also been found, that the replenishment of complement C5 by the liver and other tissues is slower in humans than in laboratory animals, including rodents and NHP. On absorption into the bloodstream, Coversin rapidly binds to circulating complement C5 forming stable inactive conjugates with an expected half-life of 63 hours, the same as that of un-complexed C5. Any excess Coversin remaining, once all C5 has been bound, is rapidly excreted via the kidneys. In planning a dosage regimen, it is important to find doses and dose intervals that will allow all C5 to be neutralized without too great a loss of unbound Coversin. The results shown in Figure 3 suggest that for most subjects/patients, following the initial AD, a single daily injection of between 25 and 50% of the AD should be sufficient to keep complement activity (CH50) below 10% of baseline, which is considered important to achieve the optimal therapeutic effect. In the dose range finding study (AK577) there were six subjects in each of Cohort 1 (30 mg once a day maintenance dose), Cohort 2 (22.5 mg once a day maintenance dose) and Cohort 3 (15 mg once a day maintenance dose), with four active subjects receiving Coversin and two subjects receiving placebo in each cohort. All subjects received an AD of four x 30 mg doses 12 hourly (or the placebo equivalent) before going on to one of three maintenance doses for a further 5-days. Cohort 4 consisted of four subjects receiving the AD of four x 30 mg doses 12 hourly followed by 19 days maintenance dose and then 7 days follow-up. In all placebo-treated subjects, CH50 results remained at around baseline levels throughout the dosing period. In contrast, the Coversin AD fully inhibited complement activity. CH50 results were inhibited by >90% from 24 h after the start of the AD period until the end of the AD period (i.e. the morning of Day 3). During maintenance dosing with 15 mg Coversin, once daily, for 5 days, complement activity remained low, but not fully inhibited (Table 2). During maintenance dosing with 22.5 and 30 mg Coversin, once daily, for 5 days, complement activity remained almost completely inhibited. For the maintenance dose of 22.5 mg Coversin, all 4 subjects had CH50 values up to about 10% of baseline at 24 h after the final maintenance dose of Coversin (Table 2). Thus, 22.5 mg Coversin, once daily, was selected as an effective dose that could minimize Coversin exposure. To further explore this effective dose, a longer dosing period was tested in Cohort 4, in which all subjects received a maintenance dose of 22.5 mg Coversin for 19 days. In all 4 subjects, complement activity was almost completely inhibited throughout the maintenance dosing period and for the 24 h after the final maintenance dose (Table 2). Recovery to baseline complement activity took approximately 5 days.

Steady state concentrations were maintained over the maintenance dosing period (Days 3–7 in Cohorts 1–3; Days 3–21 in Cohort 4), as shown by consistent pre-dose (trough) concentrations of unbound Coversin. The maintenance dose of 30 mg Coversin resulted in the highest pre-dose concentrations, whereas 22.5 mg and 15 mg Coversin resulted in lower pre-dose concentrations, which were around the Lower Limit of Qualification (LLOQ). Despite the lower exposure, 22.5 mg appeared to be as effective as 30 mg, as shown by the CH50 results. Extending the maintenance dose of 22.5 mg Coversin from 5 days to 19 days did not affect steady-state concentrations of unbound Coversin: the concentration at 12 h after final dosing was similar in both treatment groups.

In the currently on-going open label Phase II trial (AK579) in patients with PNH, five patients received an AD of 60 mg followed by 3 x 30 mg every 12 hours. They were then treated with 15 mg twice daily from Day 3 to Day 28 and it was then planned that they would move to 30 mg once daily for the remainder of the study (up to Day 90). Data obtained from the study so far has shown that all five patients achieved full ablation as measured by CH50 after the second dose and so further doses of 30 mg are now considered superfluous. Therefore, to ensure patients are not administering unnecessary large volumes the two extra doses have been dropped. In addition, for

Page 28 of 84 AKARI Confidential two of the five patients a dose of 15 mg 12-hourly was insufficient to control the LDH levels during the initiation phase and it was necessary to increase the dose to 22.5 mg 12-hourly. The earliest that the dose was changed was after 14 days of treatment. One patient received 22.5 mg twice daily Coversin for 41 days and two other patients received Coversin for 6 and 14 days respectively. The maintenance dose was planned to be 30 mg once daily, but in three out of five patients their dose was increased to 45 mg once daily. Only one patient completed the trial on 30 mg once daily. One patient with a suspected comorbidity left the trial before moving onto a once daily dose.

Based on this data, the proposed dosing for this study is an AD of 60 mg followed 12 hours later by a 30 mg dose and then 22.5 mg twice daily up to Day 28 ( $\pm$  3 days) and then 45 mg once daily up to Day 180. If the once daily dosing is deemed inadequate, then the patient may revert back to 22.5 mg twice daily dosing.

# Figure 6 Lactate dehydrogenase (LDH) level and complement activity (CH50 U Eq/mL) during treatment with Coversin for AK578

#### 2.5 Summary of Known and Potential Risks and Benefits to Human Subjects

Although there has been limited clinical experience with Coversin to date, the clinical implications of complement C5 blockade can be deduced from a combination of genetic and epidemiological studies, animal studies and experience with eculizumab *(Soliris®)*. Complement C5 deficiency in humans is a rare, familial condition caused by a variety of genetic defects including mutations in the C5 exons. Those affected have a predisposition to gram negative infections, particularly meningococcal meningitis [Densen, 1989], herpetic infections and seborrheic dermatitis [Bartholomew & Shanahan 1990].

To date (12 December 2017) Coversin has been administered to approximately 42 subjects, 32 healthy volunteers and 10 patients. In these patients Coversin has generally been found to be well tolerated. In the single ascending dose trial (VA576) the drug was well tolerated, there were no serious or severe adverse reactions and only mild injection site reactions. A total of three adverse reactions were reported in 2 of 16 subjects who received the active drug and in 1 of 8 subjects who received placebo. There was no dose relationship, three of the four AEs occurring at the lowest dose and one in the third of four ascending doses. The AEs were mild and self-limiting and consisted of light headedness (1), symptoms of a cold (1), pain in the arm related to the injection site (1) and intolerance to bright light(1).

#### Table 6Adverse Events for AK581

Overall, the adverse event profile shows few adverse events other than injection site reactions which are to be expected with daily subcutaneous injections. Going forward, AKARI proposes not to report injection site reactions which are classified as Grade 1 but only injection site reactions which are Grade 2 or above will be reported. All other adverse events regardless of grade will be reported.

A Grade 1 injection site reaction can be classified as pain, swelling or tenderness, associated with an injection when one or more of the following is also present:

- Redness surrounding the injection site and appearing within 72 hours of the injection
- Localised increase in skin temperature surrounding the injection site
- Whealing (blistering) in the vicinity of the injection site
- Itching at or around the injection site starting between 30 minutes and 72 hours of the injection [NB the injection itself may cause itching in under 30 minutes]
- Positive results of a skin biopsy (presence of increased numbers of eosinophils and/or lymphocytes)

The Common Terminology Criteria for Adverse Events (CTCAE Version 5.0) definitions should be used to classify injection site reactions of Grade 2 and above:

Grade	2	3	4	5
Description	Pain; lipodystrophy; edema; phlebitis	Ulcerations or necrosis; severe tissue damage; operative intervention indicated	Life-threatening consequences, urgent intervention indicated	Death

In a retrospective review of PNH patients on long term treatment with eculizumab (*Soliris*®), two of ninety-six patients developed meningococcal meningitis [Hillmen et al, 2013]. Currently subjects taking eculizumab (*Soliris*®) are advised to maintain prophylaxis against *Neisseria meningitidis* either by active immunization or by taking long term antibiotics or both [Dmytrijuk et al, 2008]. In this study, the anti-meningococcal measures employed in individual cases will be at the discretion of the Investigators and in accordance with local practice. In limited duration, toxicological studies with both eculizumab (*Soliris*®) and Coversin, no AEs or findings attributable to C5 blockade have been reported, but Investigators are advised to be alert for possible infectious events, even in subjects who have received meningococcal immunization.

GLP-compliant daily s.c. repeat dose studies in mice (1, 3 and 6 months) and cynomolgus monkeys (6 months) have been completed. In the 3-month mouse study (high dose group 5 mg/kg) no drug related affects were detected other than an increase in the incidence and severity of microscopic signs of inflammation detected by histopathology at the site of injection (scapular region only in mice) that were considered related to Coversin. In the 6-month mouse study high dose 6.5 mg/kg was determined to be the No Observable Adverse Event Level (NOAEL) but histopathological

inflammatory changes were observed at the site of administration. Minor immunostimulation in local lymph nodes in both sexes were observed at 6.5 mg/kg and in the spleen in males treated.

Because Coversin is a xenologous protein (derived from a tick salivary protein), there is a possibility that its chronic use may be associated with the formation of antibodies which could neutralize the effect of the drug or cause untoward adverse reactions. The immunogenicity study in mice and 58-day dosing of the 4-year-old child described above and the ongoing treatment of the Dutch PNH patient resistant to eculizumab (*Soliris*®) has gone some way to mitigating this possibility, as well as experience with other parasite derived therapeutic molecules, such as the leech-derived anticoagulant lepirudin [Greinacher and Warkentin, 2008].

The potential of Coversin to induce phototoxicity is at present unknown. For this reason, patients taking Coversin should be advised to avoid excessive exposure to sunlight or UV light (e.g. sunbeds) for the duration of the study and for five half-lives after the last administration of Coversin (5 hours).

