# **3 TRIAL OBJECTIVES AND ENDPOINTS**

# 3.1 Trial Objectives

The trial objectives of this study are to demonstrate the safety and efficacy of Coversin when given to patients with PNH and known resistance to eculizumab (*Soliris*®).

- 1) To assess the safety and tolerability of Coversin for patients between 50 and 100kg (110lb -220lb) body weight when given as a fixed maintenance dose following an initial AD and Initiation Phase.
- 2) To assess whether this dosage regimen is sufficient to control the signs and symptoms of PNH (see Endpoints).

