## 3.2 Endpoints

Primary Efficacy Endpoint:

• Reduction in serum LDH from baseline to mean of Day 43, 60, 90, 120, 150 and 180

Secondary Efficacy Endpoints:

- Change in LDH from baseline at monthly intervals after Day 28, 60, 90, 120, 150 and 180
- Change in mean Hb: baseline Day 180
- Change in FACIT score: baseline Day 28 Day 180
- Change in EQ-5D-5L QLQ C30 score: baseline Day 28 Day 180
- Number of transfusions: baseline to Day 180

Safety Endpoints:

- Frequency, type and relationship of AEs and SAEs to treatment
- Out of range laboratory parameters (hematology and chemistry)
- Vital signs (blood pressure, body temperature and pulse rate)
- ECG abnormalities baseline Day 180 (A resting pre-dose ECG taken within 7 days of first dose will be compared with ECGs taken 1- 6 hours post-dose and at 180 days of treatment with Coversin)
- Change in weight will be noted baseline and at Day 180
- Injection site reaction and lymph node inspection
- Anti-Coversin antibody production

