## 11.2 Procedures for Recording of Adverse Events

#### 11.2.1 General

All adverse events occurring during the Study (from the timepoint of signing of the Informed Consent Form (ICF) until completion of patient's study participation or premature withdrawal) observed by the Investigator or reported by the patient, whether or not attributed to the IMP, shall be recorded in patient's medical records and on the eCRF.

The following information shall be recorded:

- description,
- date of onset and end date,
- severity,
- assessment of relatedness to the IMP,
- seriousness,
- measures taken for management of the AE,
- outcome of the event.

Follow-up information should be provided as necessary.

AEs considered as being related to the IMP as judged by a medically qualified Investigator, or the Sponsor, must be followed until their resolution or when patient's status is considered as stable. All related AEs that result in a patient's withdrawal from the Study or are present at the end of the Study, should be re-evaluated and if needed followed until a satisfactory resolution occurs.

It will be left to the Investigator's clinical judgment whether or not an AE is of sufficient severity to require termination of IMP administration. A patient may also voluntarily withdraw from IMP administration due to AEs perceived as intolerable. If either of these occurs, the patient will be given appropriate care under medical supervision until symptoms cease or the condition becomes stable.

The severity of reported events shall be assessed on the following scale:

- 1 = mild
- 2 = moderate
- 3 = severe

The causal relationship of AEs to the IMP must be assessed by the Investigator, or by a medically qualified designee, in accordance with the following criteria:

Term	Definition
Unrelated	Clinical event with an incompatible time relationship to administration of the investigational medicinal product (IMP), and that could be explained by underlying disease or other drugs or chemicals or is incontrovertibly not related to the IMP
Possible related	Clinical event with a reasonable time relationship to IMP administration, and that is unlikely to be attributed to concurrent disease or other drugs or chemicals
Related	Clinical event with plausible time relationship to IMP administration and that cannot be explained by concurrent disease or other drugs or chemicals

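### Section 2.5 exempts Grade 1 injection site reactions from reporting, which contradicts Sections 3.2 and 11.2.1, and the Grade 1/Grade 2 boundary that sets the threshold is ambiguous

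*Combined protocol and SAP*

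**What the plan says.** Section 2.5, in the text after Table 6, sets a reporting rule: "AKARI proposes not to report injection site reactions which are classified as Grade 1"; only those of Grade 2 or above are to be reported. It adds: "All other adverse events regardless of grade will be reported". It also says that, ISRs apart, few adverse events were seen.

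The two grades that decide the matter are defined there:

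- Grade 1: "A Grade 1 injection site reaction can be classified as pain, swelling or tenderness", provided at least one further sign is present. The signs are redness, local warmth, whealing or blistering, itching, or a positive skin biopsy.
- Grade 2, taken from CTCAE version 5.0: "Pain; lipodystrophy; edema; phlebitis". No further sign is needed.

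Elsewhere the plan has no such exemption:

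- The synopsis makes safety the primary objective. The first aim in Section 3.1 is "To assess the safety and tolerability of Coversin for patients between 50 and 100kg".
- Section 3.2 and the synopsis list "Injection site reaction and lymph node inspection" as a safety endpoint, with no grade threshold.
- Section 11.2.1 opens its recording rule with "All adverse events occurring during the Study" and sends them to the medical records and the eCRF, whether or not they are attributed to the drug. It makes no exception for ISRs. Its mild/moderate/severe scale is not linked to the Section 2.5 grades.

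**The concern.** A site that follows Section 2.5 leaves out events that Section 11.2.1 tells it to record and that Section 3.2 counts in an endpoint. Section 2.5 itself identifies ISRs as the main kind of adverse event, so the conflict falls on the largest part of the expected profile.

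The grading makes this worse because the reporting threshold is the Grade 1/Grade 2 boundary. If one reaction can be placed on either side, whether it appears in the safety tables depends on who reads the definitions. With up to 6 patients at up to 6 centers, one site's reading can change the result. At stake are the ISR frequency and the description of low-grade tolerability.

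**Working it through.** The plan gives no ISR rate, sample-size calculation or power for this point, so there is no stated figure to reproduce.

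**1. The rules side by side.** For a reaction classified as Grade 1:

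| Place | Treatment |
|---|---|
| Section 2.5 | Not reported |
| Section 11.2.1 | Recorded in the medical records and on the eCRF |
| Section 3.2 and synopsis | Falls within an endpoint that has no grade threshold |

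No sentence says which prevails, or that reporting and recording mean different things.

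**2. The grade boundary.** Swelling is read as edema, which is an assumption.

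| Presentation | Grade 1? | Grade 2? |
|---|---|---|
| Pain or swelling, with a listed sign | Yes | Yes |
| Pain or swelling, no listed sign | No | Yes |
| Tenderness, with a listed sign | Yes | No |
| Tenderness, no listed sign | No | No |
| Redness, warmth, whealing or itching only | No | No |

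The first row can be filed as Grade 1 and left out, or as Grade 2 and reported. The last two rows have no grade. They could be left out as not Grade 2 or above, or reported as another adverse event.

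**3. Exposure against scheduled inspection.** Inputs are the regimen (Table 8), injections per dose (Table 1) and the schedule (Table 11), assuming no missed dose, re-ablation or return to twice-daily dosing.

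- Day 1: 2 + 1 = 3 injections.
- Days 2 to 28: 27 × 2 = 54.
- Days 29 to 180: 152 × 1 = 152, up to 152 × 2 = 304 if each dose is split.
- Total per completer: 3 + 54 + 152 = 209, to 3 + 54 + 304 = 361.

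Physical examinations, which include injection site inspection, fall on Days 7, 14, 21, 29, 36, 60, 90, 120, 150 and 180: ten on treatment. After Day 36 the gaps are 24 days and then 30 days. The diary items named in Sections 5.2 and 8 cover the time, date and site of injection and body temperature, with no ISR item.

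**4. Illustration of the under-count.** Let p be the share of patients with any ISR and f the share of those whose worst ISR is filed as Grade 1. Both are assumptions. For six patients, the expected number with an ISR is 6p, the expected number with one reported is 6p(1 − f), and P(none reported) = (1 − p(1 − f))^6. With p = 0.8, 6p = 4.8:

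| f | Expected reported | P(none reported) |
|---|---|---|
| 0.25 | 3.6 | 0.4^6 = 0.4% |
| 0.50 | 2.4 | 0.6^6 = 5% |
| 0.75 | 1.2 | 0.8^6 = 26% |
| 0.90 | 0.48 | 0.92^6 = 61% |

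At f = 0.75, P(none reported) is 0.875^6 = 45% for p = 0.5 and 0.75^6 = 18% for p = 1.0.

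As an extreme case, five of six patients with an ISR is 83% (exact 95% interval 36% to 99.6%). If all five had worst Grade 1 and were left out, the report would show 0 of 6 (0% to 46%).

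**The case against.** The best defense is that the exemption is worded as a proposal, sits in a background section and speaks of reporting, while Section 11.2.1 is the operative text and speaks of recording. If sites follow Section 11.2.1, the data will exist. This stands as a reason for caution, but it does not settle the conflict. The plan never draws that distinction, Section 11.2.1 itself refers to the events to be graded as reported ones, and recorded Grade 1 events could still be left out of the tables. Substantial Amendment 2 added the grading definitions to Section 2.5, so the text is not a leftover.

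Capture is also wider than ten examinations. Table 11 has an adverse event row at every visit, including Days 1, 2, 3 and 43, and home nurses attend in the first two weeks. This stands, and it limits the point to reactions that resolve between contacts.

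Several stronger inferences are tempting, and the documents do not support them:

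- *The trial cannot answer its safety objective.* Grade 2 or higher ISRs and all other adverse events are still reported, and the endpoint remains.
- *The grading is inverted, so that pain alone is reported while pain with blistering is dropped.* Pain with blistering also meets Grade 2. It is lost only if the site chooses the lower of two grades that both apply.
- *Most of the tolerability signal is removed.* No Grade 1 share is given, and on the reading above only tenderness with a sign is exclusively Grade 1.
- *The 72-hour window puts these reactions beyond scheduled inspection.* That window covers only redness and itching, and it concerns onset, not duration. With dosing every 12 or 24 hours, each on-treatment inspection follows several injections given within 72 hours.
- *The rule hides the animal safety signal.* The animal finding was microscopic inflammation with minor immunostimulation, and anti-drug antibodies are measured separately.

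**Conclusion.** The point holds as an unreconciled contradiction between Section 2.5 and Sections 3.2 and 11.2.1, together with a reporting threshold placed on overlapping and incomplete grade definitions. If sites follow Section 2.5, ISR frequency and low-grade tolerability will be under-counted and classified inconsistently. The amount cannot be stated. The 0.4% to 61% range is an illustration under an assumed 80% ISR rate, not an estimate. The overlap on pain needs no assumption; the overlap on swelling depends on reading it as edema. The matter deserves correction because it affects a safety endpoint in a trial whose primary objective is safety, and because reactions never recorded may not be recoverable later.

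**What to change.** 1. In Section 2.5, delete the Grade 1 exemption. State that ISRs of every grade are recorded on the eCRF and tabulated by grade in the ISR endpoint.
2. Make the Grade 1 and Grade 2 definitions mutually exclusive, and give a place to reactions that now have no grade, such as tenderness, redness or itching alone. Reconcile the result with the cited CTCAE row and with the mild/moderate/severe scale in Section 11.2.1.
3. If Grade 1 reactions are to be summarized from the diary card to save work, add an ISR item to the card, since none is described now.

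The cost is protocol wording, a small eCRF and diary change, more minor adverse event entries and a less favorable-looking adverse event table, for at most 6 patients. No dose or treatment rule changes.
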